3. SUMMARY OF STUDY PLAN

We will conduct a randomized double-blinded, placebo-controlled Phase II trial of statin to evaluate the impact of statin treatment on pancreatic function and inflammation in patients diagnosed with recurrent pancreatitis who are undergoing treatment at four study sites: Cedars-Sinai Medical Center (CSMC), Kaiser Southern California Permanente Medical Group (KPMC), the University of Pittsburgh (UP), and Stanford University (SU). Thirty patients will be randomized to simvastatin or placebo (20 in the simvastatin arm, 10 in the control). Assuming that ~20% of the study participants drop-out, we expect to have data on a final sample of 24 men and women (16 simvastatin, 8 control) completing the 6-month follow-up period. Clinical and research measurements will be taken at Baseline (Study Visit 1), Month 3 (Study Visit 2), and Month 6 (Study Visit 3). Three and 6 months were chosen, given that patients have variable recovery times in the order of months after an acute pancreatitis event [46]. Therefore, the repeated measures at 3 and 6 months will be essential for determining the trajectory of change in the clinical and research measurements during the recovery period.

Patients with at least two episodes of acute pancreatitis in the past 12 months will be recruited for the study. We will recruit study participants among several pools of patients: patients hospitalized for acute or chronic pancreatitis at the study sites, patients who have an upcoming appointment scheduled with a study gastroenterologist, patients referred by other physicians or staff through outpatient clinics, and patients who self-refer. All patients will receive their usual care under the guidance of their physician.

Pre-Screen Eligibility Review – Initial determination of eligibility and recruitment

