4. PARTICIPANT SELECTION

4.1 Inclusion Criteria

4.1.1 At least two episodes of acute pancreatitis in the past 12 months. Acute pancreatitis is defined as any 2 of the following: (1) Typical upper abdominal pain; (2) Elevation in serum amylase or lipase ≥ 3 times upper limit of normal; (3) Features of acute pancreatitis on cross-sectional imaging.

4.1.2 Age ≥ 18 years.

4.1.3 ECOG performance status ≤ 1 (Karnofsky $\geq 70\%$; see Appendix B).

4.1.4 Participants must have acceptable organ, hepatic and renal function as defined below:

Leukocytes	$\geq 2,500/\text{microliter}$
Absolute neutrophil count	$\geq 1,500/\text{microliter}$
Platelets	$\geq 100,000/\text{microliter}$
Hemoglobin	$> 10 \text{ g/dL}$
Total bilirubin	$\leq 3 \times$ institutional upper limit of normal (ULN)
AST (SGOT)/ALT (SGPT)	$\leq 1.5 \times$ institutional ULN
Creatinine	$< 1.5 \text{ mg/dL}$

Patients whose lab levels meet the inclusion criteria by Screen 2 will be included in the trial.

4.1.5 Women of child-bearing potential must have a confirmed negative pregnancy test result prior to enrollment.

4.1.6 The effects of simvastatin on the developing human fetus at the recommended therapeutic dose are unknown. For this reason and because statins are known to be teratogenic, women of child-bearing potential must agree to use adequate contraception (hormonal or barrier method of birth control; abstinence) prior to study entry and for the duration of study participation. Should a woman become pregnant or suspect she is pregnant while participating in this study, she should inform her study physician immediately. It is not known whether simvastatin is excreted into human milk; however, a small amount of another drug in this class does pass into breast milk. Because statins have the potential for serious adverse reactions in nursing infants, women who receive treatment with simvastatin should not breastfeed their infants.

4.1.7 Ability to understand and the willingness to sign a written informed consent document and medical release.

4.1.8 Willing and able to comply with trial protocol and follow-up.

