13. STATISTICAL CONSIDERATIONS

13.1 Study Design/Description

This is a phase II randomized, double-blinded, placebo-controlled trial of statin to evaluate the impact of statin treatment on pancreatic function and inflammation implicated in pancreatic carcinogenesis in patients with recurrent acute pancreatitis. The primary objective of this study will be to demonstrate that statins will improve pancreatic function in high-risk patients, as defined by those with two or more episodes of acute pancreatitis in the past 12 months.

The primary outcome for this study is change from baseline (Study Visit 1) at 6 months of *peak bicarbonate concentration* as measured by *ePFT*. Sample size calculations follow from computations PASS 11 (www.ncss.com). Means and standard deviations of peak bicarbonate concentrations are derived from the literature on the validity and utility of *ePFT* for diagnosis of chronic pancreatitis [56, 57]. We expect baseline peak bicarbonate levels to be 60 mEq/L in these patients with recurrent pancreatitis, with a standard deviation of 13 mEq/L. We expect the peak bicarbonate levels to increase in both simvastatin and placebo groups as the groups recover from the acute pancreatitis event, with the simvastatin group showing a greater increase to full recovery compared to the placebo group. An analytic sample size of 24 (after 20% drop out) will have 82% power to detect a statistically significant one-sided difference of 15 mEq/L (25 vs. 10 mEq/L) at an alpha level of 0.05. The anticipated changes are well within the range of

peak bicarbonate levels of patients with mild to severe pancreatitis [56, 57] whose median peak bicarbonate levels range from 40 mEq/L to 100 mEq/L.

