13.4 Primary Objective, Endpoint(s), Analysis Plan

The primary outcome for this study is change from baseline (Study Visit 1) at 6 months of peak bicarbonate concentration as measured by ePFT. For the primary endpoint, we will consider differences D(T) and D(P) for D=After-Before, for Treatment and Placebo (Control) groups respectively. Then we will use a nonparametric two-sample Wilcoxon-Mann-Whitney test to address the hypothesis H0: mean [D (T)] =mean [D (P)] versus H1: mean[D(T)] > mean[D(P)], and report a one-sided p-value, as presented in Table 3. If p<0.05 we will consider this to be evidence of activity in the simvastatin group.

Table 3. Numeric Results for Mann-Whitney Test (Uniform Distribution)									
Power	N1	N2	Ratio	Alpha	Beta	Mean1	Mean2	S1	S2
0.82	16	8	0.5	0.05	0.18	25	10	13	13
Null Hypothesis: Mean1=Mean2. Alternative Hypothesis: Mean1>Mean2. The standard deviations were assumed to be equal at 13 mEq/L.									

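### The primary test compares raw change with no allowance for time since the last acute episode; a prespecified ANCOVA would protect a 16:8 comparison against chance imbalance in recovery stage

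*Combined protocol and SAP*

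**What the plan says.** Section 3 justifies the 3- and 6-month visits on the ground that "patients have variable recovery times in the order of months after an acute pancreatitis event". Section 13.1 carries this into the sample size: "We expect the peak bicarbonate levels to increase in both simvastatin and placebo groups as the groups recover from the acute pancreatitis event". The assumed mean gains are 25 mEq/L on simvastatin and 10 mEq/L on placebo.

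The entry criterion in section 4.1 is "At least two episodes of acute pancreatitis in the past 12 months", with no minimum or maximum time since the latest one. Section 3 recruits inpatients, clinic patients, referrals and self-referrals, and allows the Screen 2 ePFT, which serves as baseline, up to 8 weeks after consent.

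Section 13.2 randomizes 2:1 at each site and names no patient-level stratification factor. For the primary endpoint, section 13.4 states "we will consider differences D(T) and D(P) for D=After-Before", applies a two-sample Wilcoxon-Mann-Whitney test without covariates, and judges activity on a one-sided p below 0.05. Regression appears only in section 13.5, for secondary variables and as hypothesis generation. No planned analysis uses time since the last episode.

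**The concern.** The plan itself names recovery from the acute event as a source of change in the primary endpoint. It then admits patients whose baseline test may follow the last episode by weeks or by most of a year. A patient tested early in recovery plausibly has more to gain over six months than one tested late, whichever arm they are in. Time since the last episode is fixed before randomization, so it is a legitimate covariate.

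The whole trial rests on one p-value with 8 expected placebo completers. If the arms turn out to differ in recovery stage, readers will ask whether the result reflects simvastatin or recovery. An adjustment added after the data are seen would look data-driven, whereas one written now would not. The unadjusted test also gives up whatever precision the covariates could supply.

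**Working it through.** **Inputs from the plan (sections 13.1, 13.3, 13.4):** 16 and 8 patients analysed, difference 15 mEq/L, SD 13 mEq/L in each arm, one-sided alpha 0.05, stated power 82%, uniform distribution.

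**Input not in the plan:** R², the share of the variance of change explained by time since the last episode. I assume 0.1 to 0.4 and show the range.

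**1. The plan's own figure.** The standard error of the arm difference is 13 × √(1/16 + 1/8) = 13 × 0.433 = 5.63. The noncentrality is 15/5.63 = 2.665. With 22 degrees of freedom and a Mann-Whitney efficiency of 1 for a uniform distribution, power is 82.5%, which matches the stated 82%. On normal data, with the exact one-sided cut-off (U ≥ 92, true level 0.046), simulation gives the Wilcoxon about 79%.

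**2. Chance of imbalance.** The standardised difference between arms in any baseline covariate has SD 0.433. So P(|difference| > 0.5 SD) = 2 × Φ(−0.5/0.433) = 2 × Φ(−1.155) = 0.248, or about one trial in eight in each direction.

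**3. Effect on the estimate.** The shift at a 0.5 SD imbalance is 0.5 × √R² × 13. The SD of the shift over randomizations is 13 × √R² × 0.433, which gives the chance of a shift of 7.5 mEq/L (half the target) or more in either direction.

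| R² (assumed) | Shift at 0.5 SD | Share of 15 | SD of shift | Chance of 7.5 or more |
|---|---|---|---|---|
| 0.1 | 2.1 | 14% | 1.8 | under 0.1% |
| 0.2 | 2.9 | 19% | 2.5 | 0.3% |
| 0.4 | 4.1 | 27% | 3.6 | 3.5% |

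**4. Effect on the test.** Simulation: normal data, total SD held at 13, 100,000 trials per case. The two middle columns condition on an imbalance above 0.5 SD in the direction named. The ANCOVA column is overall power with two covariates and total R² as in the first column.

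| R² | Wilcoxon false-positive rate, imbalance favours simvastatin | Wilcoxon power, imbalance favours placebo | Two-covariate ANCOVA power, overall |
|---|---|---|---|
| 0.1 | about 11% | 64% | 83% |
| 0.2 | 14–15% | 56% | 86–87% |
| 0.4 | 20–21% | 42–44% | 93% |

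Under the same imbalances the two-covariate ANCOVA keeps a false-positive rate of about 5%, and its power when placebo is favoured is about 80%, 84% and 91%. Averaged over all randomizations, the Wilcoxon's false-positive rate stays between 4.4% and 4.7% and its power at 79% whatever the R².

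**5. Cost if the covariates are useless (R² = 0).** Unadjusted t-test 82.5%, one covariate about 81%, two covariates about 79%. The two-covariate model is then some 3.5 points below the t-test and level with the Wilcoxon on normal data.

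**The case against.** The strongest reply is that nothing in the plan is invalid. Randomization keeps the one-sided error at or below 5%, and any recovery-stage variation inside the assumed SD of 13 is already counted in the power. This stands. The problem is conditional: it concerns the one allocation that will actually occur, and precision forgone.

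A reader might also infer that imbalance could create or hide most of the simvastatin effect. The documents do not support that. They give no R², and even at 0.4 a shift of half the target or more has only a 3.5% chance. Nor does section 13.1 make recovery the only driver, since it credits simvastatin with the additional 15 mEq/L.

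Third, varying recovery times do not show that calendar time predicts change well. Patients may recover at different rates, and new episodes on study (section 8.3 foresees them) cannot be captured by a pre-baseline interval. Baseline bicarbonate may already carry the signal. If so, adding the interval lowers power slightly: from 84.3% to 82.6%, 89.7% to 88.2% and 94.5% to 93.4% at R² of 0.1, 0.25 and 0.4. The gain is therefore conditional, but the possible loss is small.

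Finally, Screen 1 confirms at least two episodes in 12 months; the plan does not say that their dates are captured as data. That also stands, and the date field has to be added.

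**Conclusion.** The point holds as one of conditional bias and efficiency. The plan names recovery as a source of change, leaves recovery stage open at baseline, and neither stratifies nor adjusts for it. At 16:8 there is a 25% chance of an imbalance above 0.5 SD. For an assumed R² of 0.1 to 0.4, an imbalance of 0.5 SD is worth 2.1 to 4.1 mEq/L (14 to 27% of the target), and imbalances beyond 0.5 SD carry a conditional false-positive rate of about 11 to 21% when they favour simvastatin.

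These sizes rest on three assumptions: the R² range, a linear relation with normal errors, and an SD of change of 13. Section 13.1 introduces 13 as the SD of baseline levels and the documents give no SD of change; the shifts in mEq/L scale with it. It would be wrong to conclude that the planned Wilcoxon test is invalid or that a positive result would be mostly recovery. The change is worth making before unblinding but is not a condition for the trial to proceed.

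**What to change.** In section 13.4, prespecify a single ANCOVA of 6-month peak bicarbonate on arm, baseline peak bicarbonate, and time from the last acute episode to the Screen 2 ePFT. State in advance the scale on which that interval enters. Report the unadjusted Wilcoxon test alongside. If the sponsor prefers to keep the Wilcoxon as primary, name this ANCOVA as the prespecified supporting analysis, so that only one test is primary.

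Add the date of the last acute episode to the case report form, taken from the history reviewed at Screen 1, and tabulate the interval by arm.

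The cost is plan wording, one recorded date and one derived variable, with no change to eligibility, visits or sample size. Statistically it costs two degrees of freedom. Power is about 83 to 93% at a total R² of 0.1 to 0.4. If neither covariate predicts the outcome it is about 79%, no worse than the Wilcoxon on normal data.

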- c) Findings on MRI/MRCP: major duct abnormalities (Cambridge Classification 3 or greater) (**Table 2**).

Table 2. Cambridge classification for chronic pancreatitis

Grade	Main pancreatic duct	Side branches
Normal (Grade 0)	Normal	Normal
Equivocal (Grade I)	Normal	<3 Abnormal
Mild (Grade II)	Normal	≥3 Abnormal
Moderate (Grade III)	Abnormal	>3 Abnormal
Severe (Grade IV)	Abnormal with at least one of the following: Large cavity >10 mm Duct obstruction Intraductal filling defect Severe dilatation or irregularity	>3 Abnormal

Because statins are known to be teratogenic, women of child-bearing potential will be required to have a pregnancy test during Screen 2. Women who are pregnant will be excluded from the trial. Patients with lab results outside the eligibility range will also be excluded.

Screen 2 eligible/consented patients will be registered and randomized to the study drug (either simvastatin or placebo). The Screen 2 EUS and ePFT results will be used as Study Visit 1 baseline measurements.

Study Visits

Study Visit 1 (Baseline measurements and initiation of the intervention). The first study visit will occur 0-14 days after Screen 2. The following procedures will be performed during this visit:

- a) Review of medical history, medications, and laboratory test results; vital signs assessment, symptom assessment, and ECOG performance status
- b) Blood collection for clinical labs and research
- c) Collection of a fecal specimen (self-collected at home)
- d) Interviewer-administered comprehensive questionnaire (demographics, risk factor and clinical assessment (Appendix E)
- e) Self-administered QLQ-C30 and QLQ-PAN28(CP) to assess quality of life and pain level (Appendix D)
- f) Review of inclusion /exclusion criteria
- g) Dispense study drug and review instructions for how to take it
- h) Dispense study diary and review instructions for how to complete it

Study Visit 2. The first follow-up visit will occur 3 months (\pm 1 month) after initiation of the intervention. The following procedures will be performed during this visit:

- a) Review of medical history, medications, and laboratory test results; physical exam, vital signs assessment, symptom assessment, and ECOG performance status
- b) Blood collection for clinical labs and research
- c) Endoscopic pancreatic function test (ePFT) and simultaneous esophagogastroduodenoscopy (EGD)
- d) Collection of a fecal specimen (self-collected at home)

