Study visits will be scheduled at 3 months (\pm 1 month) and 6 months (\pm 1 month) to avoid protocol violations. A day or two prior to the scheduled follow-up visit, the participant will be contacted by telephone to confirm or reschedule his/her visit. Patients who develop intercurrent pancreatitis will receive usual medical care by their gastroenterologist, and their next study visit will be rescheduled if necessary. The study coordinator will have a database which tracks active participants who do not have a scheduled visit or who have missed their targeted visit date. Study visits will be rescheduled for up to 2 months until the participant is considered lost to follow-up.

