7. CLINICAL EVALUATIONS AND PROCEDURES

7.1 Schedule of Events

Procedure	Pre-Screen ¹	Screen 1 ²	Screen 2 ³	Study Visit 1 ⁴	Months 1-3	Study Visit 2 ⁵	Months 4-6	Study Visit 3 ⁶	Follow-Up
Assess eligibility	X	X	X						
Informed consent form and HIPAA authorization		X							
Registration and randomization to simvastatin or placebo			X						
Review medical history, medications, and lab test results		X	X	X		X		X	
Review CT and MRI results		X							
Blood Hematology: Complete Blood Count with Differential (CBDF)			X			X		X	
Blood Chemistry: Comprehensive Metabolic Panel (CMPL)			X			X		X	
Pancreatic fluid via endoscopic pancreatic function test (ePFT)			X			X		X	
Endoscopic ultrasound (EUS)			X					X	
Esophagogastroduodenoscopy (EGD)						X			
Urine pregnancy test ⁷			X			X		X	
Demographics (date of birth, race, ethnicity, education)				X					
Physical exam			X			X		X	
Vital signs assessment, measure weight, symptom assessment, and ECOG performance status			X	X		X		X	
Blood test: Lipid Panel				X		X		X	
Blood test: Hemoglobin A1C (HbA1C)				X				X	
Blood test: Creatine phosphokinase (CPK)				X					
Collect blood specimen for				X		X		X	

Procedure	Pre-Screen ¹	Screen 1 ²	Screen 2 ³	Study Visit 1 ⁴	Months 1-3	Study Visit 2 ⁵	Months 4-6	Study Visit 3 ⁶	Follow-Up
research ⁸									
Fecal specimen (self-collected)				X		X		X	
Risk factor questionnaire				X				X	
QLQ-C30 and QLQ-PAN28(CP)				X		X		X	
Imaging studies, as needed				X		X		X	
Review eligibility criteria				X		X			
Dispense study agent and diary				X		X			
Collect study agent and diary						X		X	
Review study diary						X		X	
Assess compliance					X	X	X	X	
Assess adverse events					X	X	X	X	X
Telephone contact ⁹	X	X	X	X	X	X	X	X	X

¹ Pre-Screen eligibility review by clinical research staff to determine initial eligibility. Research staff will review medical records of patients hospitalized for pancreatitis, and of patients who have an upcoming appointment with a study gastroenterologist. For patients who respond to direct advertisement and outside referrals who call to request more information (whose medical records are not available), research staff will describe the study, field questions, and assess potential eligibility using an IRB-approved phone script.

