7.2.3 Screen 2 – Final determination of eligibility, Registration, and Randomization

Consented patients who are eligible after Screen 1 will undergo the following procedures within 8 weeks after consent to rule out advanced chronic pancreatitis and pregnancy. Patients will be instructed to fast overnight (8 hours) before the endoscopic testing.

1. Clinical labs for a Complete Blood Count with Differential (CBDF) and a Comprehensive Metabolic Panel (CMPL) will be done to confirm that laboratory levels for acceptable organ, hepatic, and renal function are within the eligibility requirements. See Appendix A for Clinical Laboratory Minimum Test Requirements. If a patient's lab results within 35 days before the Screen 2 visit are available in the medical record and are within eligibility range, their blood will not be drawn at the Screen 2 visit. Otherwise, the patient's blood will be drawn to confirm eligibility.
2. Pregnancy test for women of child-bearing potential. Women who have had a hysterectomy, both ovaries removed, or a tubal ligation will not be required to have a pregnancy test.
3. Physical exam including vital signs assessment, symptom assessment, and ECOG performance status
4. Endoscopic ultrasound (EUS)
5. Endoscopic pancreatic function test (ePFT)

Based on Screen 2 results, patients with EUS evidence of advanced chronic pancreatitis, patients with lab results outside the eligibility range, and women who are pregnant will be excluded from the trial. Patients with EUS evidence of advanced chronic pancreatitis will not undergo the ePFT. See Section 3. Summary of Study Plan for advanced chronic pancreatitis diagnostic criteria.

Consented patients who qualify for the study after the Screen 2 eligibility evaluations will be registered and randomized to the study drug (simvastatin or placebo). The Screen 2 EUS and ePFT results will be used as Study Visit 1 baseline measurements. The pancreatic fluid will be used to measure secretin-stimulated peak bicarbonate concentration; cytokines, chemokines, and adhesion molecules.

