7.2.4 Study Visit 1 – Baseline Testing and Initiation of the Statin Intervention

Study Visit 1 (Baseline measurements) will occur 0-14 days after Screen 2. Participants will be told to fast for 8 hours before the study visit. Fasting instructions will be provided to participants prior to their study visit, and participants will receive a phone call reminder the day before the visit to fast overnight. The following procedures will be performed during this visit:

1. Review medical history, medications, and laboratory test results
2. Measure height and weight and symptom assessment
3. Vital signs assessment: blood pressure, heart rate, respiratory rate, and oral temperature
4. ECOG performance status

5. Blood collection for clinical labs (approximately 10 mL). Laboratory blood tests will be done for a Lipid Panel, hemoglobin A1C, and creatine phosphokinase (CPK) to establish baseline levels prior to initiating the study agent. CBDF and CMPL lab results from the Screen 2 eligibility visit will be used to establish patient-specific references prior to initiation of therapy. If blood tests were not done at the Screen 2 visit for a CBDF and CMPL; and lab results within 30 days prior to this visit for these tests are not available in the medical record, a CBDF and CMPL will be done at this visit. See Appendix A for Clinical Laboratory Minimum Test Requirements.
6. Blood collection for research purposes (26 mL): 6 mL will be collected for measurement of protocol-specific biomarkers (serum concentrations of cytokines, chemokines, and adhesion molecules), and 20 mL will be banked for DNA extraction and future studies.
7. Fecal specimen for measurement of fecal elastase. A stool collection kit and instructions will be provided to the participant before the scheduled visit. The specimen will be self-collected at home. The participant will receive a phone call reminder the day before the visit to collect the fecal specimen and bring it to the study visit.
8. Interviewer-administered questionnaire to obtain demographic information (date of birth, detailed race and ethnicity, education); medical history, including pancreatic diseases and diabetes; medications, including analgesics and antibiotics; physical activity; history of alcoholic beverage consumption; tobacco smoking history; and anthropometry
9. Self-administered QLQ-C30 and QLQ-PAN28(CP) to assess quality of life and pain level
10. Review of inclusion /exclusion criteria

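### Randomization at Screen 2 precedes the Visit 1 eligibility review and first dose by up to 14 days, so avoidable losses fall after randomization

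*Combined protocol and SAP*

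**What the plan says.** Section 3 (Screen 2) states: "Screen 2 eligible/consented patients will be registered and randomized to the study drug (either simvastatin or placebo". The Schedule of Events in Section 7.1 marks the row "Registration and randomization to simvastatin or placebo" under Screen 2, and Section 7.2.3 agrees. The interval to first dose is also in Section 3: "The first study visit will occur 0-14 days after Screen 2".

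Item 10 of the Visit 1 list in Section 7.2.4 is "Review of inclusion /exclusion criteria"; item 11 is dispensing. The endoscopic tests are not repeated at that visit: "The Screen 2 EUS and ePFT results will be used as Study Visit 1 baseline measurements".

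Sections 13.5 and 13.8 keep every randomized participant in the assigned arm and in the primary evaluation. Section 8.4 lists ineligibility as a reason to leave the study, but no section says how to handle a patient who is randomized and then fails the Visit 1 review.

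On laboratory tests, Section 7.2.3 lets a chart result replace the Screen 2 draw: "If a patient's lab results within 35 days before the Screen 2 visit are available in the medical record" and are in range, no blood is taken. Section 7.2.4 calls for a blood count and metabolic panel at Visit 1 if none was drawn at Screen 2 and "lab results within 30 days prior to this visit for these tests are not available in the medical record". Sections 4.1.4 and 4.2.12 judge the laboratory criterion by Screen 2. The blood-specimen paragraphs of Sections 3 and 7.6, however, give confirming eligibility to continue as one purpose of the study-visit blood tests, Visit 1 included.

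On new attacks, Section 4.4 says: "Patients who develop intercurrent pancreatitis will receive usual medical care by their gastroenterologist, and their next study visit will be rescheduled if necessary".

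**The concern.** A patient is best randomized at the last moment before treatment at which eligibility can still be decided. Here an eligibility review, and up to two weeks of ordinary patient turnover, sit between randomization and the first capsule. The Visit 1 review covers history, medications and laboratory results, so it can turn up a newly started prohibited drug or an intercurrent illness. Anyone lost at that point counts among the 30 randomized but is unlikely to supply the 6-month ePFT that the primary test needs. The analysis is planned on 16 and 8 patients, so each such loss matters.

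The gap also affects the baseline. Participants are selected for recurrent attacks, and Section 13.1 expects bicarbonate to rise as patients recover from an attack. If an attack falls between the Screen 2 ePFT and the first dose, the baseline no longer describes the patient at the start of treatment. Section 11.1.1 starts adverse event recording only once the Visit 1 assessments are complete, so such an attack need not appear in the adverse event data.

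**Working it through.** **1. The plan's own power.** Inputs from Sections 13.1 and 13.4: 16 and 8 analysed, difference 15 mEq/L, SD 13 in both arms, one-sided alpha 0.05, Mann-Whitney test under a uniform distribution (efficiency 1.0 relative to the t test).

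- Noncentrality = 15 / (13 × √(1/16 + 1/8)) = 15 / 5.63 = 2.66, with 22 degrees of freedom.
- Power = 0.825, which reproduces the stated 0.82.
- Sample size: 24 / (1 − 0.20) = 30, as stated.

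**2. Losses in the gap.** The documents give no figure, so 1 to 3 of 30 is an assumption. Suppose that these losses come on top of the 20% dropout. Analysed numbers are then 20 × (1 − f) × 0.8 and 10 × (1 − f) × 0.8, where f is the fraction lost in the gap.

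| Lost in gap | Analysed | Power | Randomized to keep 24 |
|---|---|---|---|
| 0 | 16.0 : 8.0 | 0.825 | 30 |
| 1 of 30 | 15.5 : 7.7 | 0.813 | 32 |
| 2 of 30 | 14.9 : 7.5 | 0.800 | 33 |
| 3 of 30 | 14.4 : 7.2 | 0.786 | 34 |

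If gap losses are already within the six dropouts expected in Section 13.6, power stays at 0.825. The plan does not say which is meant.

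**3. Attacks in the gap.** With an assumed constant rate r per year and a gap of g days, the chance per patient is 1 − exp(−r × g / 365.25).

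| Rate per year | 7 days: chance, of 30 | 14 days: chance, of 30 |
|---|---|---|
| 0.5 | 0.95%, 0.3 | 1.9%, 0.6 |
| 1 | 1.9%, 0.6 | 3.8%, 1.1 |
| 2 | 3.8%, 1.1 | 7.4%, 2.2 |
| 3 | 5.6%, 1.7 | 10.9%, 3.3 |

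**4. Effect of gap attacks on the test.** The Wilcoxon test was simulated with 16 and 8 patients and uniform data (20,000 trials per setting). In both arms alike, 2% to 10% of patients had their change score lowered by 10 to 30 mEq/L. The fractions and shifts are assumptions. Power fell from about 0.75 without attacks to between 0.75 and 0.64. Type I error stayed at 0.044 to 0.049. The simulated reference is below 0.82; that is a separate matter, and only the contrast is used here.

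**5. Laboratory windows.** With a 14-day gap, a chart result taken 17 days before Screen 2 is 17 + 14 = 31 days old at Visit 1. Chart results from 17 to 35 days before Screen 2 therefore pass at Screen 2 but prompt a new draw at Visit 1 if no later result exists. That draw comes after randomization and on the dispensing day, and no text says whether dispensing waits for the result.

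**The case against.** The strongest reply is that Screen 2 is by its own title the final eligibility step. The Schedule of Events separates assessing eligibility (up to Screen 2) from reviewing the criteria (Visits 1 and 2), and the Visit 2 review is plainly a conformance check. On that reading few patients would be removed at Visit 1. This limits the likely number of failures. It does not cover withdrawals or patients who become unfit, and it does not explain why the criteria are reviewed immediately before dispensing.

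A reader might infer that eligibility rests on results 49 days old at first dose, or that an abnormal Visit 1 result means dosing outside the criteria. The documents do not support either. Section 7.2.4 requires a new draw in exactly the case that would give 49 days, and Sections 4.1.4 and 4.2.12 judge laboratory values by Screen 2. The 35-day and 30-day windows may also serve different purposes, eligibility and a patient reference. Nor does a high Visit 1 ALT meet the hepatotoxicity rule in Section 5.6, which requires a relation to the study agent. No share of patients using chart results is given, so nothing can be said about how many are affected. What stands is that the passages do not agree on what the Visit 1 result is for.

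A reader might also take Section 4.4 to allow Visit 1 to slip by two months after an attack. That limit belongs to the rule for loss to follow-up, and Visit 1 has its own 14-day window.

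Finally, gap attacks are a small part of the attacks to be expected: 14 days is about 8% of a six-month treatment period (14 / 183), and Section 8.3 accepts attacks on treatment. That is fair. The entry criterion of two past attacks is also not a floor on the future rate, hence the range used above.

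**Conclusion.** The point holds as a modest and avoidable inefficiency. Randomization precedes the last eligibility review and the first dose by up to 14 days, and losses in that interval fall on the all-randomized set. If 1 to 3 of 30 are lost beyond the planned dropout, power falls from 0.825 to between 0.813 and 0.786. Between 0.3 and 3.3 of 30 participants would have a gap attack under the assumed rates (2.2 at two attacks a year and 14-day gaps). Loss counts, attack rates and shift sizes are all assumptions.

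Two stronger conclusions are tempting and not supported. First, the all-randomized rule is not broken: leaving the study as ineligible is not exclusion from analysis, and Sections 13.5 and 13.8 keep the patient in. Second, gap attacks do not bias the comparison. They precede any drug, so they are balanced by arm in expectation, and they cost power and precision rather than validity.

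**What to change.** Move registration and randomization to Study Visit 1, after the eligibility review and before dispensing, and amend Sections 3, 4.4, 7.1, 7.2.3 and 7.2.4 to match. Gap failures then become screen failures, and 30 randomized with 24 analysed keeps the planned power. Section 6.8 already requires only that registration come before treatment.

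Reconcile the laboratory passages: the 35-day window against the 30-day window, and eligibility judged by Screen 2 against Visit 1 tests meant to confirm it. The aim is that any blood count or metabolic panel needed for eligibility is available before randomization, using the 10 mL Screen 2 draw that Section 3 already provides.

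Moving randomization does not by itself correct the baseline of a patient who has a gap attack and stays eligible. For that, record every attack between the Screen 2 ePFT and the first dose, and examine those patients in a sensitivity analysis. No repeat ePFT and no new exclusion is asked for; a repeat would mean another sedated procedure.

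The cost is protocol wording and logistics. The pharmacy must receive the assignment on the day of Visit 1, within the weekday registration hours of 9:30 to 5:00 Central Time, and some patients will have blood drawn at Screen 2 instead of Visit 1. If randomization stays at Screen 2, the plan should at least state how patients who fail at Visit 1 and baselines that precede an attack are handled.
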